2.4 Sample Size

Sample size is formed by a total of 64 healthy male and female subjects 18 to 55 years old. In SAD, up to 40 adult subjects. Five cohorts (Cohorts 1 to 5) of 8 subjects each (40 subjects in total) will receive a single dose of CVN766 or matching placebo orally.

In MAD, up to 24 adult subjects. Three cohorts (Cohorts 1 to 3) of 8 subjects each (24 subjects in total) will receive a daily dose of CVN766 orally.

Since there is no formal statistical hypothesis testing, no formal sample size calculation has been performed. The proposed sample sizes for each study part are typical for studies at this phase of development and are deemed sufficient to evaluate the study objectives for this Phase 1 study.

2.5 Randomization

In SAD, five cohorts (Cohorts 1 to 5) of 8 subjects each (40 subjects in total) will receive a single dose of CVN766 or matching placebo. Within each cohort, 6 subjects will be randomly assigned to receive CVN766, and 2 subjects will receive matching placebo. For each cohort, a sentinel group of 2 subjects will initially be randomized to receive CVN766 or placebo (1:1 ratio) on the same day to allow for the assessment of any acute adverse events (AEs). The remaining 6 subjects (5 CVN766 and 1 placebo) will be randomized and dosed at least 24 hours after the sentinel group, following a review of available safety data by the Sponsor and Principal Investigator (PI).

In MAD, three cohorts (Cohorts 1 to 3) of 8 subjects each (24 subjects in total), will be enrolled. Within each cohort, 6 subjects will be randomly assigned to receive CVN766, and 2 subjects will receive matching placebo.

3. STATISTICAL CONSIDERATIONS

Data will be handled and processed per the sponsor's representative (Novotech) Standard Operating Procedures (SOPs), which are written based on the principles of good clinical practice (GCP).

Each study part will be presented separately.

3.1 General Considerations

All data collected on the electronic case report form (eCRF) will be presented in the data listings and will be listed and sorted by treatment arm, participant number and visit, where applicable. All descriptive summaries will be presented by treatment group and nominal visit/time point (where applicable).

Unless otherwise stated, the following methods will be applied:

- **Continuous variables:** Descriptive statistics will include the number of non-missing values (n), arithmetic mean, standard deviation (SD), median, minimum, and maximum values.

The minimum and maximum values will be displayed to the same decimal precision as the source data, the arithmetic mean, SD, and median values will be displayed to one more decimal than the source data for the specific variable.

The appropriate precision for derived variables will be determined based on the precision of the data on which the derivations are based, and statistics will be presented in accordance with the above-mentioned rules.

- **PK data:** The actual blood sampling dates and times relative to dosing time will be listed by participant and nominal sampling time, with time deviation calculated, for all participants with available plasma concentration data, including participants excluded from the PK population. Individual (for each participant) and mean CVN766 concentrations over time will be displayed graphically in linear and semi-logarithmic plots of CVN766 concentrations versus time. The actual collection time will be used for individual plasma CVN766 concentration curves and the nominal time will be used for the plots of mean plasma CVN766 concentration curves.

For PK concentration data, the number of non-missing values, number of below limit of quantification (BLQ) values, arithmetic mean, standard deviation, median, minimum, maximum, coefficient of variation (CV%), geometric mean and geometric coefficient of variation (geo CV%) values will be presented. For the calculation of summary statistics, unrounded data will be used and reported to three significant figures with the exception of n, n BLQ, and CV% which will be presented to the nearest integer and one decimal place, respectively.

For PK parameter data, the number of non-missing values, arithmetic mean, standard deviation, median, minimum, maximum, coefficient of variation (CV%), geometric mean and geometric coefficient of variation (geo CV%) values will be presented. Individual PK parameters will be presented to three significant figures with the exception of λ_z which will be presented to four decimal places.

- **Categorical variables:** Descriptive statistics will include counts and percentages per category. The denominator in all percentage calculations will be the number of participants in the relevant analysis population with non-missing data, unless specifically stated otherwise. Percentages will be displayed to one decimal place. Proportions will be displayed in 3 decimal places.
- **Repeat/unscheduled assessments:** Only values collected at scheduled study visits/time points will be presented in summary tables. If a repeat assessment was performed, the result from the original assessment will be presented as the result at the specific visit/time point. All collected data will be included in the data listings.
- **Assessment windows:** All assessments will be included in the data listings and no visit windows will be applied to exclude assessments that were performed outside of the protocol specified procedure windows.

- **Result display convention:** Results will be center aligned in all summary tables and listings. Participant identifiers visit and parameter labels may be left-aligned if required.
- **Date and time display conventions:** The following display conventions will be applied in all outputs where dates and/or times are displayed:

Date only: YYYY-MM-DD

Date and time: YYYY-MM-DD HH:MM

If only partial information is available, unknown components of the date or time will be presented as 'NK' (not known), i.e., '2016-NK-NK'. Times will be reported in military time.

3.2 Key Definitions

The following definitions will be used:

- **Baseline:** The baseline value is defined as the last available valid (quantifiable continuous or categorical value), non-missing observation for each participant prior to first study drug administration. Repeat and unscheduled assessments will be included in the derivation of the baseline values.
- **Change from Baseline:** The change from baseline value is defined as the difference between the result collected/derived at a post-baseline visit/time point and the baseline value.

The change from baseline value at each post-baseline visit/time point will be calculated for all continuous parameters using the following formula:

$$\text{Change from Baseline Value} = \text{Result at Visit/Time Point} - \text{Baseline Value}$$

The change from baseline value will only be calculated if the specific post-baseline visit/time point result and the baseline value for the parameter are both available and will be treated as missing otherwise.

- **Study day:** The study day of an event is defined as the relative day of the event starting with the date of the first study drug administration (reference date) as Day 1 (there will be no Day 0).

The study day of events occurring before the first study drug administration will be calculated as:

$$\text{Study Day} = (\text{Date of Event} - \text{Date of First Study Drug Administration})$$

For events occurring on or after Day 1, study day will be calculated as:

$$\text{Study Day} = (\text{Date of Event} - \text{Date of First Study Drug Administration}) + 1$$

Study days will only be calculated for events with complete dates and will be undefined for events that are 'Ongoing' at the end of the study.

Relative days compared to an alternative reference point will be calculated similarly, but the alternative starting reference start date will be used instead of the date of the first study drug dosing.

- **Actual Time from First Dose (hours)** = (Date/Time of PK Sample collection) – (Date/Time of First Dose on Day 1)
- **Actual Time from Last Dose (hours)** = (Date/Time of PK Sample collection) – (Date/Time of Last Dose), where the last dose = Most Recent Previous Dose.
- **Actual Time Deviation (hours)** = (Actual PK Sample Collection Time Post Dose) – (Scheduled PK Sample Collection Time Post Dose).
- **Prior Medications:** Prior medications are defined as any medication where the use was stopped prior to the first administration of the study medication.
- **Concomitant Medications:** Concomitant medications are defined as any medication (other than the study drug) that was used at least once after the first administration of the study drug.

Medications that were stopped on the same date as the first study drug administration will be defined as concomitant medications. If a clear determination cannot be made (partial medication end dates) the medication will be classified as concomitant

- Treatment Emergent Adverse Events (TEAEs): are defined as adverse events that occurred within 30 days (onset date – last date of dose + 1 ≤ 30) after study drug administration.

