2.1.1 Part 1: SAD is the single-dose regimen and Fasted- Fed Crossover

Approximately 40 healthy male or female subjects will be enrolled in 1 of 5 single-dose cohorts (designated as S1 through S5, respectively) in an ascending fashion. An optional Cohort 3a may be added in parallel to SC3 for additional safety and tolerability evaluation. Cohort S3a dose level will be consistent with Cohort S3 (45 mg planned) in a fasted condition only and without lumbar puncture, aligned with other SAD cohorts. Each cohort will consist of 8 subjects randomized to CVN766 or placebo, whereby 6 subjects will receive a single oral dose of CVN766 suspension, and 2 subjects will receive a matching placebo suspension under overnight fasted conditions. Sentinel dosing (1 subject to receive CVN766 and 1 subject to receive placebo) will be used in each cohort to ensure adequate safety and tolerability evaluation prior to administering CVN766 or placebo to the remainder of the subjects within the cohort. The planned dose levels will be 5, 15, 45, 125, and 250 mg CVN766. Each following dose level may be higher, lower, or remain the same as the preceding cohort. Additional cohort(s) may be added if deemed necessary by the SRG to fully characterize the safety and tolerability of CVN766. To assess the effect of food on CVN766 bioavailability in suspension formulation, the single-dose administration will be repeated in a single cohort (S3) after ingestion of a standardized high-fat, high-calorie meal. Once the safety of the S3 cohort dose level has been assessed, the S3 cohort subjects will return to the clinic (no sooner than 14 days after their prior dose, or at least 4 half-lives, has lapsed based on preliminary PK data, whichever is longer). They will receive the same dose as before, administered after ingesting a standardized breakfast. Subjects will finish at least approximately 85% of their breakfast within 30 minutes and receive an investigational product 30 minutes (\pm 5 minutes) after beginning the meal. Sentinel dosing will not be required for subjects returning to the clinic for the fed regimen. If the CVN766 PK parameters in the fasted S3 cohort reveal poor absorption with inconclusive results, the fed cohort will be deferred until a higher dose level.

[figure not shown]
On Day 1, subjects will undergo safety monitoring and PK sampling from blood plasma through 72 hours post-dose and, for cohort S3 (fasted) only, from CSF via lumbar puncture at 3 hours post-dose

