11.3 Vital Signs

The following vital signs measurements will be taken at the time points specified in the Schedule of Events (refer to the Protocol):

- Pulse (beats/min);
- Systolic Blood Pressure (SBP) (mmHg)
- Diastolic Blood Pressure (DBP) (mmHg)
- Respiratory Rate (breaths/min)
- Body Temperature (°C)

All vital signs data collected at scheduled and unscheduled visits will be included in the listings, but only results collected as scheduled visits will be included in the summary tables.

Triplicate orthostatic vital signs (blood pressure and heart rate) will be recorded at baseline (Check-in Day -1) 15 minutes apart (the average will be used to determine eligibility).

The parameter names that will be used in the outputs will comprise of the test name and the unit of measure, for example, 'Systolic Blood Pressure (mmHg)'. Parameters will be sorted in the order that the measurements were collected in on the Vital Signs eCRF page within the tables and listings.

Vital signs measurements will present summary statistics for the results at the baseline and each scheduled post-baseline visit for each of the parameters in Supine and Standing position. In addition, summaries will be presented for the change from baseline values at each scheduled post-baseline visit in Supine and Standing position (continuous descriptive analysis). The average of triplicate vital signs in Supine and Standing position will be used as baseline for HR and BP.

In addition, vital signs and postural changes, the individual subject level at each time point between the two positions in which readings are taken (Supine vs Standing) will be reported. At each timepoint standard descriptive stats for HR, sBP and dBP postural data will be reported.

Further, a categorical tabulation for number (percentage) of subjects per time point (and overall categories for any post-exposure timepoint for each parameter separately and for the 2 BP measures together) for the following clinically changes will be created:

- Drop in dBP of ≥ 10 mmHg when moving from supine to standing
- Drop in sBP of ≥ 20 mmHg when moving from supine to standing
- Increase in HR of ≥ 30 bpm when moving from supine to standing

The decimal precision to which the summaries for each parameter will presented will be based on the maximum number of decimals to which the results were reported on the eCRF.

11.4 12-Lead Electrocardiogram (ECG)

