12. CHANGES TO THE PLANNED ANALYSIS

Changes to planned analysis include:

- The following endpoint has been added in relation to PK analysis: To potentially identify significant difference between gender of PK parameters in plasma.
- Standard descriptive stats for HR, sBP and dBP postural data will be reported using a categorical tabulation for number (percentage) of subjects per time point in relation to:
 - Drop in dBP of ≥ 10 mmHg when moving from supine to standing
 - Drop in sBP of ≥ 20 mmHg when moving from supine to standing
 - Increase in HR of ≥ 30 bpm when moving from supine to standing
- For triplicate vital sign at Day -1/ baseline average value will be used.
- Pharmacodynamic Exploratory Endpoints will not be included in the SAP.
- To date, RNA/DNA Analysis has not been conducted, and no data is available for the SAP.
- No suicidal assessments were conducted as part of this study; therefore, this will not be included in data listings.
- It was decided that screen failure data will not be entered in the EDC, as it is the site/CRO practice for phase 1 studies because there are hundreds of SFs, and this data is not imperative for any analysis.

- **INTERIM AND FINAL ANALYSIS**

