	Day 2	xx (xx.x%)	xx (xx.x%)	xx (xx.x%)	xx (xx.x%)
				
CVN766 125 mg (N=xx)	Baseline	xx (xx.x%)	xx (xx.x%)	xx (xx.x%)	xx (xx.x%)
	Day 1	xx (xx.x%)	xx (xx.x%)	xx (xx.x%)	xx (xx.x%)
	Day 2	xx (xx.x%)	xx (xx.x%)	xx (xx.x%)	xx (xx.x%)
...					

Source: Listing 16.2.8.3.2

[1] Baseline is defined as the last available, valid, non-missing observation prior to first study drug administration.
 Number of participants at each visit (n) will be used as the denominator for the calculation of all percentages.
 [2] Number of participants with non-missing values at that visit.
 ET = Early Termination.

Programing Note:

Add following treatment columns;
 CVN766 45 mg, CVN766 125 mg, CVN766 250 mg, Overall CVN766, Overall Placebo and Overall.

Table 14.3.5.1.1 Summary of Vital Signs SAD (Safety Population)

Position: Supine Measurements
 Parameter: Heart rate (beats/min)

Treatment	Visit	Timepoint	n	Actual Value					Change from Baseline[1]					
				Mean	SD	Median	Minimum	Maximum	n	Mean	SD	Median	Minimum	Maximum
CVN766 5 mg (N=xx)	Baseline[1]		xx	xx.x	xx.x	xx.x	xx	xx	N/A					
	Day 1	0.5 hours	xx	xx.x	xx.x	xx.x	xx	xx	xx	xx.x	xx.x	xx.x	xx	xx
		1 hours	xx	xx.x	xx.x	xx.x	xx	xx	xx	xx.x	xx.x	xx.x	xx	xx
		2 hours	xx	xx.x	xx.x	xx.x	xx	xx	xx	xx.x	xx.x	xx.x	xx	xx
		4 hours	xx	xx.x	xx.x	xx.x	xx	xx	xx	xx.x	xx.x	xx.x	xx	xx
		8 hours	xx	xx.x	xx.x	xx.x	xx	xx	xx	xx.x	xx.x	xx.x	xx	xx
		12 hours	xx	xx.x	xx.x	xx.x	xx	xx	xx	xx.x	xx.x	xx.x	xx	xx
	Day 2	24 hours	xx	xx.x	xx.x	xx.x	xx	xx	xx	xx.x	xx.x	xx.x	xx	xx
		36 hours	xx	xx.x	xx.x	xx.x	xx	xx	xx	xx.x	xx.x	xx.x	xx	xx
	Day 3	48 hours	xx	xx.x	xx.x	xx.x	xx	xx	xx	xx.x	xx.x	xx.x	xx	xx
		60 hours	xx	xx.x	xx.x	xx.x	xx	xx	xx	xx.x	xx.x	xx.x	xx	xx
	Day 4	72 hours	xx	xx.x	xx.x	xx.x	xx	xx	xx	xx.x	xx.x	xx.x	xx	xx
	Day 8		xx	xx.x	xx.x	xx.x	xx	xx	xx	xx.x	xx.x	xx.x	xx	xx
	ET		xx	xx.x	xx.x	xx.x	xx	xx	xx	xx.x	xx.x	xx.x	xx	xx
...												

Source: Listing 16.2.9.1.1

[1] Baseline is defined as the last available, valid, non-missing observation prior to first study drug administration.

N/A = Not Applicable. SD = Standard Deviation.

ET = Early Termination.

Programming Note:

Add following treatment columns;

CVN766 5 mg, CVN766 15 mg, CVN766 45 mg(Fasted), CVN766 45 mg(Fed), CVN766 125 mg, CVN766 250 mg, Overall CVN766, Overall Placebo Placebo(Fed) and Overall

Overall CVN766 will not contain CVN766 45 mg(Fed)

Overall Placebo will not contain Placebo (Fed) from S3 Cohort

Repeat for Position: Supine, Standing

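### Safety changes in the S3 fed period are taken from a baseline before the fasted dose, and the HR/BP baseline rule of Sections 11.3 and 12 is not carried into Section 3.2 or the shells

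*SAP*

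**What the plan says.** **General rule.** Section 3.2 sets baseline as the last valid "non-missing observation for each participant prior to first study drug administration". It then fixes the change: "The change from baseline value is defined as the difference between the result collected/derived at a post-baseline visit/time point and the baseline value". Repeat and unscheduled readings count towards baseline. No separate rule is given for a second dosing period.

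**Two periods in S3.** Section 2.1.1 has the S3 participants dosed fasted. Later, "the S3 cohort subjects will return to the clinic (no sooner than 14 days after their prior dose", or after at least 4 half-lives if that is longer, and they are dosed again after a meal.

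**Shells.** The programming notes of the SAD laboratory, vital-sign and ECG tables list the fed group as its own column ("CVN766 45 mg(Fasted), CVN766 45 mg(Fed), CVN766 125 mg"), together with Placebo (Fed). The footnote under most of these tables reads: "Baseline is defined as the last available, valid, non-missing observation prior to first study drug administration".

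**HR and BP.** Section 11.3 places triplicate orthostatic readings at check-in on Day -1 and says: "The average of triplicate vital signs in Supine and Standing position will be used as baseline for HR and BP". Section 12 lists this among the changes to the planned analysis: "For triplicate vital sign at Day -1/ baseline average value will be used".

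**The concern.** A change from baseline in the Fed column is read as what happened after the fed dose. Under Section 3.2 it is measured from before a different, earlier dose. Anything that moved between the periods, such as ordinary drift or a residual effect of the fasted dose, is added to the fed response. The adjacent Fasted column carries no such component. The same applies to laboratory shifts, where the starting category would come from the earlier period.

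The HR/BP issue is separate. The text and the shells select different records as baseline: a mean of three Day -1 readings, or the last reading before dosing. A programmer working from the shells and one working from Section 11.3 would produce different HR and BP changes from the same data.

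**Working it through.** The SAP states no figure for this point, so the check is a comparison of its sections.

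**S3 Fed baseline**

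1. *Does 'first' mean the fasted dose?* Section 11.1 names period 2 (Fed) explicitly when it means the first administration in that period, and assigns TEAEs by period. Section 9 assigns concomitant medications by onset period. Section 3.2 carries no period qualifier, so its plain meaning is the first dose in the study, which for S3 is the fasted dose.

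2. *How far back is that?* Section 2.1.1 requires at least 14 days between doses. The S3 visit list gives Days 21, 22, 23, 24 and 28, which are Days 1, 2, 3, 4 and 8 plus 20. If Day 21 is the fed dosing day, the doses are 21 - 1 = 20 days apart. That reading is inferred from the pattern and is not stated. The explicit 14-day minimum is enough for the point.

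3. *Which outputs are touched?* In SAD, the Fed columns and the baseline footnote occur together in the haematology/coagulation and chemistry summaries and shifts, the vital-sign and orthostatic summaries, and the ECG summaries. The SAD urinalysis shell and the categorical orthostatic shells carry no baseline footnote. Section 3.7 introduces its group list as being for medications, history and AEs only, but the programming notes of these safety tables name the Fed groups, so the columns will be produced.

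4. *How many participants?* One cohort of 8: 6 active and 2 placebo. Section 3.7 and the shells exclude the fed assessments from Overall CVN766 and Overall Placebo.

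5. *What does the choice of baseline do?* For one participant, let S and F be a fasted-period and a fed-period value, B1 the value before the fasted dose and B2 a value before the fed dose.
   - Fed change as planned: F - B1 = (F - B2) + (B2 - B1). The second term is the between-period shift.
   - Fed minus fasted change as planned: (F - B1) - (S - B1) = F - S. The common baseline cancels.
   - Fed minus fasted change with period baselines: (F - B2) - (S - B1) = (F - S) - (B2 - B1).

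   The Fed change itself therefore contains B2 - B1, while the within-participant contrast of the two changes is simply the raw difference.

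**HR/BP baseline**

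| Place in SAP | Record used as baseline |
|---|---|
| 11.3 | Mean of the Day -1 triplicate |
| 12 | Mean of the Day -1 triplicate |
| 3.2 | Last valid value before first dose |
| Footnotes, vital-sign and orthostatic tables | Last valid value before first dose |
| Listing 16.2.9.1.1 (heart rate) | Flag [1] on Day 1 pre-dose, not on Day -1 |

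The two rules pick different records whenever a valid Day 1 pre-dose reading exists, and the listing shell has a row for one. The planned total is 40 + 24 = 64 participants, not counting the optional S3a.

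**The case against.** A single drug-free baseline is a defensible choice. It cancels in any within-participant comparison of fed with fasted, and the summaries print actual values beside the changes. The washout is at least 14 days or 4 half-lives, whichever is longer, which limits residual drug; with first-order elimination, 4 half-lives leave (1/2)^4 = 6.25% of the starting concentration. All of this stands. It limits the harm, but the Fed change column still carries the between-period shift, and nothing in the SAP says that this was intended.

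On HR and BP, the specific rule in 11.3, confirmed in 12, would ordinarily govern over the general rule in 3.2. That is a fair reading. But the SAP does not state the precedence, and the shells and the listing flag apply the other rule.

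Four stronger inferences are tempting and are not supported:

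- *The fed and fasted columns cannot be compared.* The cancellation above shows that they can, for participants with both periods.
- *A valid pre-fed value is being discarded.* The S3 visit list goes from Day 8 to Day 21 without a separate check-in visit, and assessment times are left to the protocol, which is not shown. Such a value may or may not exist for each parameter.
- *The change scores are more variable by a known factor.* The ratio is sqrt((1 - r_far)/(1 - r_near)), where the two r are within-participant correlations over the longer and the shorter interval. With r_near = 0.8, values of r_far of 0.5, 0.6, 0.7 and 0.8 give 1.58, 1.41, 1.22 and 1.00. The SAP gives no correlation, so no inflation figure can be claimed.
- *Every safety table is affected.* MAD tables are untouched by the S3 point, and in SAD only the Fed columns are.

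**Conclusion.** The concern holds, with limited reach. As written, the plan measures S3 fed-period changes and laboratory shifts from before the fasted dose, at least 14 days before the fed dose. This affects descriptive safety columns for 6 active and 2 placebo participants. Change from baseline is listed under other endpoints in Section 2.3. The primary endpoints are percentages of participants with TEAEs or clinically significant abnormalities and use no baseline. PK and the food-effect estimates are unaffected, as are the pooled active and placebo columns. The size of the between-period shift cannot be derived from the SAP.

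The HR/BP inconsistency is also real and reaches all cohorts. It is a matter of precedence and alignment, since two body sections already give the same answer.

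The conclusion rests on reading 'first study drug administration' in 3.2 literally, which the wording of Section 11.1 supports. It does not depend on Day 21 being the fed dosing day. Both points should be corrected before programming.

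**What to change.** 1. Add to Section 3.2: *For S3 Fed, baseline is the last valid non-missing value collected on return to the clinic for Period 2 (check-in or pre-dose) and before the Period 2 dose; if none was collected, the value is shown without a change or shift.* Tying the rule to the return visit matters. A looser phrase such as 'after Period 1' would clash with Section 11.1, where Period 1 runs up to the Period 2 dose. Read as 'after the fasted dose', it could admit a Day 4 or Day 8 post-dose value.
2. Amend the SAD table footnotes so that the Fed columns cite this baseline.
3. State in Section 3.2 that Section 11.3 overrides it for HR and BP. Align the vital-sign and orthostatic table footnotes and the [1] flag in Listing 16.2.9.1.1.
4. For S3, use the same type of HR/BP record in both periods: the check-in triplicate mean if it is repeated in Period 2, otherwise the pre-dose reading in each period for the fed/fasted display. Otherwise one column starts from a mean of three readings and the other possibly from a single reading.

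The cost is SAP and shell wording plus a derivation flag. No new data are needed.
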